8.3.2 Reasons for Removal From Study

Reasons for removal of a subject from the study are:

- decision by sponsor
- withdrawal of consent from study
- death
- lost to follow-up

At the time of the primary analysis and/or at the end of the long-term follow-up portion of the study, sites may be asked to conduct searches of public records, such as those establishing survival status, if available, to obtain survival data for any subject for whom the survival status is not known.

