10.7.4 Exploratory Biomarker Endpoints Analysis

The investigation of lymphocytes subset, cytokines, and chemokines measurement will be part of a separate biomarker analysis plan by scientists from the Clinical Biomarkers and Diagnostics (CBD) group.

11. Literature Citations / References

Clopper CJ and Pearson ES. The use of confidence or fiducial limits illustrated in the case of the binomial, *Biometrika*. 1934; 26(4):404-413.

12. Appendices

Appendix A. Handling of Dates, Incomplete Dates and Missing Dates for Adverse Events and Concomitant Medications

The following data will be imputed using the following algorithm:

- Adverse Events
- Concomitant Medications

Table 1. Imputation Rules for Partial or Missing Start Dates

Start Date		Stop Date						missing
		Complete: yyyymmdd		Partial: yyyymm		Partial: yyyy		
		< 1 st dose	≥ 1 st dose	< 1 st dose yyyymm	≥ 1 st dose yyyymm	< 1 st dose yyyy	≥ 1 st dose yyyy	
Partial: yyyymm	= 1 st dose yyyymm	2	1	2	1	n/a	1	1
	≠ 1 st dose yyyymm		2		2	2	2	2
Partial: yyyy	= 1 st dose yyyy	3	1	3	1	n/a	1	1
	≠ 1 st dose yyyy		3		3	3	3	3
Missing		4	1	4	1	4	1	1

1 = Impute the date of first dose
 2 = Impute the first of the month
 3 = Impute January 1 of the year
 4 = Impute January 1 of the stop year

Note: If the start date imputation leads to a start date that is after the stop date, then do not impute the start date.

Imputation rules for partial or missing stop dates:

Initial imputation

- For partial stop date mmyyyy, impute the last of the month.
- For partial stop date yyyy, impute December 31 of the year.
- For completely missing stop date, do not impute.
- If the stop date imputation leads to a stop date that is after the death date, then impute the stop date as the death date.
- If the stop date imputation leads to a stop date that is before the start date, then there is a data error and do not impute the stop date. (ie. set the stop date as missing).

Imputation rules for partial or missing death dates:

- If death year and month are available but day is missing:
- If mmyyyy for last contact date = mmyyyy for death date, set death date to the day after the last contact date.
- If mmyyyy for last contact date < mmyyyy for death date, set death date to the first day of the death month.

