- If mmyyyy for last contact date > mmyyyy for death date, data error and do not impute.
- If both month and day are missing for death date or a death date is totally missing, **the death date will be imputed as the day after the date last known to be alive.**

Note that the last contact date refers to the last contact (ie, a visit or an assessment) with patient instead of family members. Last contact date would be derived from the latest patient visit/assessment date.

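### SAP Appendix A discards a recorded year of death and, when the month is known, can date a death before the subject was last known alive; the overall effect is probably small and the fix is short

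*SAP*

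**What the plan says.** The death-date rules are at the end of SAP Appendix A and have two parts.

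- **Month and day missing, or no date at all.** The trigger is "If both month and day are missing for death date or a death date is totally missing", and then "the death date will be imputed as the day after the date last known to be alive". A year-only date and no date are handled alike.
- **Year and month known, day missing.** For a last contact in the same month: "If mmyyyy for last contact date = mmyyyy for death date, set death date to the day after the last contact date". For a last contact in an earlier month: "set death date to the first day of the death month". Last contact is restricted to "the last contact (ie, a visit or an assessment) with patient instead of family members", and "Last contact date would be derived from the latest patient visit/assessment date".

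The OS definition in SAP Section 6 uses a different reference date: survivors are censored when last known alive.

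The protocol has several sources of survival information besides seeing the patient. Under Section 7.6, subjects who did not respond or who relapsed are followed by telephone for survival status, possibly by the treating physician. Section 8.1 lists family or friends, other physicians and medical records. Section 8.3.2 adds that "sites may be asked to conduct searches of public records". SAP Section 6 (Death Date) expects some deaths to be collected from public records after a subject has left the study.

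Appendix A is headed as covering adverse events and concomitant medications. SAP Section 9.3 sends endpoint missing-data rules to Section 10, which has no death-date rule.

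**The concern.** An imputation rule should fill in what is missing without contradicting what is recorded. These rules can fail that in two ways: the first part can return a year other than the recorded one, and the second can return a date on which the subject was still known to be alive. The same appendix keeps a known year elsewhere: adverse event and medication stop dates with only a year go to 31 December of that year, and start dates with only a year, other than the year of first dose, generally go to 1 January.

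Death is an event for OS and RFS and the outcome for 100-day mortality after alloHSCT. Compared with the earliest date the records allow, the errors are always towards earlier death, so they do not cancel. Partial dates are foreseeable where a death is found by a record search after the site has stopped trying to reach the subject, which Protocol Section 7.6 allows after three failed attempts.

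**Working it through.** The plan gives no figure on this point, so there is none to reproduce. The check applies each rule to worked dates, then gauges the aggregate effect under stated assumptions.

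**Year-only branch.** Rule: death = last known alive + 1 day. Earliest date consistent with the record: the later of that date and 1 January of the recorded year.

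| Last known alive | Recorded year | Rule gives | Earliest consistent date | Error, at least |
|---|---|---|---|---|
| 15 Mar 2018 | 2019 | 16 Mar 2018 | 1 Jan 2019 | 291 days |
| 1 Aug 2019 | 2020 | 2 Aug 2019 | 1 Jan 2020 | 152 days |
| 15 Nov 2019 | 2020 | 16 Nov 2019 | 1 Jan 2020 | 46 days |
| 1 Feb 2020 | 2020 | 2 Feb 2020 | 2 Feb 2020 | 0 days |

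Contacts are every 3 months ± 1 month. An early contact at month 2 and a late one at month 7 are (6 + 1) − (3 − 1) = 5 months apart. The second row is therefore about the limit while contacts are kept. The first row needs a subject out of contact for longer.

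For 100-day mortality, take a transplant on 1 July 2019, last known alive 1 September 2019, and death recorded in 2020. The rule gives 2 September 2019, day 63, which counts as a death within 100 days. The recorded year shows survival to at least 1 January 2020, day 184.

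**Month-known branch.** These cases require that the later known-alive date came from someone other than the patient.

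| Last patient contact | Known alive | Death recorded | Rule gives | Before known-alive date by |
|---|---|---|---|---|
| 3 Mar 2020 | 25 Mar 2020 | Mar 2020 | 4 Mar 2020 | 21 days |
| 10 Dec 2019 | 20 Mar 2020 | Mar 2020 | 1 Mar 2020 | 19 days |

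The largest possible conflict is 31 − 1 = 30 days.

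**Aggregate effect on OS (illustrative).** Assumptions: exponential OS with median 6.1 months (study MT103-211, Protocol Section 2.5.2); contacts kept, with gaps of 2, 3 or 5 months; first infusion at a random point in the year; 2% to 20% of deaths with only the year known. This share is assumed, because the documents give none. Simulated median OS in months, rule / year floor, against a true 6.10:

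| Deaths affected | 2-month gap | 3-month gap | 5-month gap |
|---|---|---|---|
| 2% | 6.08 / 6.08 | 6.07 / 6.07 | 6.05 / 6.06 |
| 5% | 6.05 / 6.05 | 6.03 / 6.04 | 5.99 / 6.01 |
| 10% | 6.00 / 6.01 | 5.96 / 5.97 | 5.89 / 5.91 |
| 20% | 5.91 / 5.92 | 5.83 / 5.85 | 5.68 / 5.73 |

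Among year-only deaths, 7.5%, 11.0% and 17.2% were dated before the recorded year at the three gaps. A median of 9.8 months (study MT103-206) gave 7.7%, 11.3% and 18.2%. The year floor recovered between 0 and 0.05 months of the median in every setting.

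**100-day mortality under the rule.** Assumptions: constant hazard, contact gaps of 61, 91 or 122 days. With a true rate of 10%, the estimate rose by 0.1 to 0.4 percentage points at 5% affected and 0.4 to 1.5 at 20%. With a true rate of 20%, it rose by 0.2 to 0.7 and 0.8 to 2.7 points.

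These simulations do not cover the month-known branch or subjects out of contact for longer than the gaps shown.

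**The case against.** The strongest reply is that this hardly matters. OS, RFS and 100-day mortality are descriptive secondary endpoints in a single-arm study, and the shift is against the drug. Most of it comes from dating death to the day after last known alive, which the correction keeps. At 3-month gaps and 5% affected, the correction moves the median only from 6.03 to 6.04 months. All of this stands and limits the point to a small one.

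Four stronger readings are tempting, and the documents do not support them.

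- A reader might infer that the year-only sentence can itself place death before a known-alive date. It cannot, since it always gives the day after last known alive. Only the month-known branch can.
- A reader might infer that every subject followed by telephone is exposed in the month-known branch. Protocol Table 9 lists survival status as a scheduled long-term assessment, and the SAP note contrasts the patient with family, not clinic with telephone. A call that reaches the patient can be read as a contact. The fault needs information from someone else.
- A reader might infer impossible survival times. Both month-known results fall after the last patient contact, so OS stays positive; the conflict is with another record.
- A reader might infer that 100-day mortality is exposed through telephone-only non-responders. That analysis is limited to subjects in remission who go to transplant, and Protocol Section 7.6 gives them marrow and hematology assessments while in remission. Exposure comes mainly through year-only dates and later loss of contact.

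It can also be said that Appendix A is not written for OS. That is fair: its use for OS is an inference from its being the only death-date rule in the SAP. It is a reason to state the scope, not a defence of the rule.

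**Conclusion.** The point holds as two small faults in a stated rule. A recorded year of death can be overridden, by up to about 5 months while contacts are kept and by more after contact is lost. A death with known month can be dated up to 30 days before a date the subject was known alive, if that later information did not come from the patient.

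The documents do not support a claim that the OS or 100-day results will be materially biased. The direction is clear, but the size depends on how many death dates are partial, which is not given. Under an assumed 2% to 20%, with contacts kept, simulated median OS falls from 6.10 to between 6.08 and 5.68 months, and little of that is due to the lost year. The primary CR/CRh* analysis uses no death date. The conclusion also rests on the inference that Appendix A feeds OS, RFS and 100-day mortality. The change is worth making because a prespecified rule should not contradict the data it is applied to.

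**What to change.** Replace the death-date rules in SAP Appendix A with one set that uses the date last known alive throughout:

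- Year known, month and day missing: the later of 1 January of that year and the day after last known alive.
- Year and month known, day missing: the later of the first of that month and the day after last known alive.
- Wholly missing: the day after last known alive, as now.

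Keep the existing treatment as a data error when the reference date falls after the recorded period of death. State that the rule applies to OS, RFS and 100-day mortality, or place it in Section 10, where Section 9.3 sends the reader for endpoint rules. Report the number of imputed death dates, by branch, with the OS results, so that a reader can judge how much of the remaining early shift matters.

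The cost is a few lines of SAP text and a small programming change, with no new data.

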Appendix B. Laboratory Grading and Notable Vital Sign Values

Laboratory Values

Safety laboratory values below a distinct limit (eg. detection limit, documented as “< [limit]”) will be substituted by half of the limit and values above a distinct limit (documented as “> [limit]”) will be substituted by the limit itself for all analyses.

A Grade (based on CTC AE version 4.0 [v4.03: June 14, 2010]) will be assigned to each laboratory result as detailed in Table 2. Depending on the toxicity definition, the same result may be assigned to two grading for deviations towards higher or lower values. In case no lower limit of normal is provided for the absolute lymphocyte, neutrophils or leukocyte counts it will not be differentiated between grade 1 and grade 0 results for these parameters. Values not meeting any of the criteria will be assigned a grade 0.

Table 2. Grading of Select Laboratory Parameters

Laboratory Parameter [Unit]	Grade 1	Grade 2	Grade 3	Grade 4
Lymphocytes [G/L]	0.8 - < LLN	0.5 - < 0.8	0.2 - < 0.5	< 0.2
Neutrophils [G/L]	1.5 - < LLN	1.0 - < 1.5	0.5 - < 1.0	< 0.5
Leukocytes [G/L]	3.0 - < LLN	2.0 - < 3.0	1.0 - < 2.0	< 1.0
Platelets [G/L]	75 - < LLN	50 - < 75	25 - < 50	< 25
Hemoglobin [g/L]*	100 - < LLN	80 - < 100	< 80	not defined
Albumin [g/L]	30 - < LLN	20 - < 30	< 20	not defined
AST*	> ULN – 3*ULN	> 3*ULN – 5*ULN	> 5*ULN – 20*ULN	> 20*ULN
ALT *	> ULN – 3*ULN	> 3*ULN – 5*ULN	> 5*ULN – 20*ULN	> 20*ULN
GGT	> ULN – 2.5*ULN	>2.5*ULN – 5*ULN	> 5*ULN – 20*ULN	> 20*ULN
Bilirubin	> ULN – 1.5*ULN	>1.5*ULN – 3*ULN	> 3*ULN – 10*ULN	> 10*ULN
Fibrinogen [^]	%change of BL <25% or 0.75*LLN - < LLN	25%- <50% of BL or < 75*LLN – 0.5*LLN	50% - <75% of BL or < 0.5* LLN – 0.25*LLN	>= 75% of BL or < 50mg/dL or < 0.25*LLN
Corrected Calcium [mmol/L]*	2.0 - < LLN	1.75 - < 2.0	1.5 - < 1.75	< 1.5
Potassium [mmol/L]*	not defined	3.0 - < LLN	2.5 - < 3.0	< 2.5
Lipase	> ULN – 1.5*ULN	> 1.5*ULN – 2.0*ULN	> 2.0*ULN – 5.0*ULN	> 5.0*ULN
Amylase	> ULN – 1.5*ULN	> 1.5*ULN – 2.0*ULN	> 2.0*ULN – 5.0*ULN	> 5.0*ULN

BL: baseline value, LLN: Lower limit of normal, ULN: Upper limit of normal

*: Clinical criteria from CTC AE 4.0 grading were not considered in order to assign grades

[^]: In case of conflicting criteria the higher grade will be assigned, % change only used when baseline is <LLN

Vital Signs

Notable values for vital signs are defined according to the following table:

Table 3. Notable Abnormalities of Vital Signs

Vital Sign		Notable Abnormalities
Pulse rate (bpm)		>120 <50
Blood pressure (mmHg)	Systolic	≥160 ≤90
	Diastolic	≥105 ≤50
Weight (kg)	change from baseline ≥10% (in both directions)	
Body temperature (°C)		> 39

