6.8 Guidelines for Common Toxicities

6.8.1 Hydration During the Treatment Period

Because of the high tumor load the subjects should receive adequate hydration according to institutional guidelines.

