The investigator is responsible for reviewing laboratory test results and determining whether an abnormal value in an individual study subject represents a clinically significant change from the subject’s baseline values. In general, abnormal laboratory findings without clinical significance (based on the investigator’s judgment) are not to be recorded as adverse events. However, laboratory value changes that require treatment or adjustment in current therapy are considered adverse events. Where applicable, clinical sequelae (not the laboratory abnormality) are to be recorded as the adverse event.

The Investigator is expected to follow reported adverse events until stabilization or reversibility.

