10.6 Safety Analyses

10.6.1 Adverse Events

The Medical Dictionary for Regulatory Activities (MedDRA) version 20.0 or later will be used to code all adverse events (AE) to a system organ class and a preferred term. AEs of interest (EOI) categories will be based on search strategies defined by medical coding. Treatment-emergent adverse events are events with an onset after the administration of the first dose of Blinatumomab.

The subject incidence of AEs will be summarized for all treatment-emergent AEs, serious AEs, AEs leading to withdrawal of Blinatumomab, fatal AEs and EOI.

Subject incidence of all treatment-emergent AEs, serious AEs, AEs leading to withdrawal of IP, and fatal AEs will be tabulated by system organ class and preferred term in descending order of frequency; similar summaries will be repeated for EOs. Time to onset of selected EOs (infection, **cytokine release syndrome** and neurologic events) may also be summarized **with descriptive statistics. Duration of selected EOs will be summarized by KM methods and the descriptive statistics for resolved events (number of subjects; number of events; number of days experiencing events: mean, SD, median, Q1, Q3, min, max) and unresolved events (number of subjects, number of events) of selected EOs should also be provided.**

A summary of treatment-emergent AEs will be tabulated by system organ class, preferred term, and worst grade.

Subgroup analyses (if there is a medical or regulatory rationale) will be presented by system organ class and preferred term in descending order of frequency.

The number and percentage of subjects with antibody formation to blinatumomab will be summarized. In addition, changes in vital sign and laboratory parameters will be summarized.

Subject incidence of all disease related events, fatal disease related events, serious disease related events, and disease related events leading to withdrawal from blinatumomab, will also be provided.

Extent of exposure to blinatumomab will be summarized using descriptive statistics. Percentage of subjects and number of cycles with doses held and dose reductions will be calculated.

These analyses will be performed using subjects in the SAS.

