10.6.2 Laboratory Test Results

Shift tables between the worst post-baseline and baseline grades for select laboratory parameters defined in [Appendix B](#). Plots or other summaries overtime will be presented for select laboratory parameters including immunoglobulin, platelets, and liver parameters (alanine transaminase, aspartate transaminase, γ -glutamyl transferase, alkaline phosphatase, and total bilirubin) for subjects in the Safety Analysis Set. **The subject incidence of potential cases of Hy's Law will be summarized.**

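### SAP Appendix B grades potassium and corrected calcium only on the low side, so high values share the grade 0 cell with in-range values in the laboratory shift tables

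*SAP*

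**What the plan says.** The grading rules are in SAP Appendix B, Table 2. The potassium row is "Potassium [mmol/L]* not defined 3.0 - < LLN 2.5 - < 3.0 < 2.5" and the corrected calcium row is "Corrected Calcium [mmol/L]* 2.0 - < LLN 1.75 - < 2.0 1.5 - < 1.75 < 1.5", with columns running from grade 1 to grade 4. The asterisk on both rows means only that the clinical parts of the CTCAE definitions were set aside.

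Two sentences above the table govern its use. One says that, depending on the toxicity definition, "the same result may be assigned to two grading for deviations towards higher or lower values". The other is the fallback: "Values not meeting any of the criteria will be assigned a grade 0". The scale is stated to be CTCAE 4.0 (v4.03).

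SAP section 10.6.2 plans "Shift tables between the worst post-baseline and baseline grades for select laboratory parameters defined in" Appendix B. It also plans plots or other summaries over time for selected parameters, naming immunoglobulin, platelets and liver tests. Section 10.6.1 adds that "changes in vital sign and laboratory parameters will be summarized", without saying how.

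**The concern.** The appendix foresees a high and a low grading for the same result, but supplies no high-side criteria for potassium or corrected calcium. The fallback then sends every high value to grade 0, where it cannot be told apart from an in-range value. Neither row is labelled as hypokalemia or hypocalcemia, so a reader of the finished shift table would not know that grade 0 includes high values.

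What is at stake is the clarity of one safety output. The graded shift table does not depend on an investigator deciding that a laboratory value is worth recording. For these two analytes it cannot show a rise of any size. The protocol does expect a heavy disease burden (section 6.8.1: "Because of the high tumor load the subjects should receive adequate hydration according to institutional guidelines"), so chemistry results will be read with some care.

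**Working it through.** There is no planned figure to reproduce. The check is to apply the stated rules to test values.

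**Inputs.** Thresholds and the grade 0 fallback come from SAP Appendix B. The documents do not give LLN, so it is an assumption here: 3.3, 3.5 and 3.7 mmol/L for potassium; 2.1, 2.15 and 2.2 mmol/L for corrected calcium.

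**Rules as written**, for a value x in mmol/L:

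- Potassium: grade 4 if x < 2.5; grade 3 if 2.5 ≤ x < 3.0; grade 2 if 3.0 ≤ x < LLN; otherwise 0.
- Corrected calcium: grade 4 if x < 1.5; grade 3 if 1.5 ≤ x < 1.75; grade 2 if 1.75 ≤ x < 2.0; grade 1 if 2.0 ≤ x < LLN; otherwise 0.

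**Results**, identical for every assumed LLN:

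| Analyte | Values (mmol/L) | Grades |
|---|---|---|
| Potassium, low | 2.4, 2.8, 3.2 | 4, 3, 2 |
| Potassium, mid-range to high | 4.2, 5.5, 6.5, 7.5, 9.0 | 0, 0, 0, 0, 0 |
| Corrected calcium, low | 1.4, 1.6, 1.9, 2.05 | 4, 3, 2, 1 |
| Corrected calcium, mid-range to high | 2.3, 2.9, 3.2, 3.6, 4.0 | 0, 0, 0, 0, 0 |

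**What the shift table would show:**

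- Potassium from 4.2 at baseline to a worst value of 3.2: shift 0 to 2.
- Potassium from 4.2 to 7.5: shift 0 to 0, the same cell as a subject who stays at 4.2.
- Potassium of 4.2 at baseline, then both 2.8 and 7.5 on study: worst grade is max(3, 0) = 3, so only the low excursion is seen.
- Corrected calcium from 2.3 to 3.6: shift 0 to 0.

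**Does any row use the two-direction sentence?** Table 2 has 15 rows. Nine are graded downward (lymphocytes, neutrophils, leukocytes, platelets, hemoglobin, albumin, fibrinogen by its LLN multiples, corrected calcium, potassium). Six are graded upward (AST, ALT, GGT, bilirubin, lipase, amylase). 9 + 6 = 15, so no analyte has both directions and the sentence has nothing to act on.

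**Fibrinogen, clerical check.** The LLN multiples bounding grades 1 to 4 read, in order, 0.75 to 1, then 75 down to 0.5, then 0.5 down to 0.25, then below 0.25. The 75 breaks the sequence and looks like 0.75 with the leading characters lost. Taken literally, a value at 1 × LLN lies below 75 × LLN and would be grade 2. Fibrinogen is not in protocol Table 11, whose coagulation column holds only aPTT and INR.

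**The case against.** The strongest reply is that high values are captured elsewhere. Protocol section 9.2.2.1 says "laboratory value changes that require treatment or adjustment in current therapy are considered adverse events", and changes judged clinically significant are recorded too. Adverse events are graded by CTCAE 4.03 and tabulated by system organ class, preferred term and worst grade (SAP 10.6.1). A potassium high enough to need treatment should therefore be reported. This stands, and it limits the point to the shift tables. It is not a full substitute: the same protocol section generally leaves out abnormal values without clinical significance and, where applicable, records the clinical sequelae and not the laboratory abnormality. The general laboratory summary is unspecified, and the over-time summaries do not name electrolytes, although that list is open-ended.

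A second reply is that the two-direction sentence is permissive and the table covers selected parameters only, so a low-side scale may be deliberate. That is possible. But nothing in the table says so, and the fallback still merges high with in-range values.

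Some stronger readings are tempting, and the documents do not support them:

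- A reader might infer that the SAP reports high values as normal. It does not use that word; grade 0 means that no criterion was met.
- A reader might infer that the tables are wrong for all 120 subjects. Only a subject with a high value at baseline or later can be placed misleadingly, and the documents give no frequency.
- A reader might infer that creatinine, uric acid and phosphorus, collected under Table 11, ought to be graded. Table 2 is expressly a selection, so leaving them out breaks no rule.
- A reader might infer from the hydration passage that the protocol flags a potassium rise. It mentions tumor load and hydration, not potassium or calcium.

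**Conclusion.** The point holds within narrow limits. For potassium and corrected calcium, every value at or above LLN is grade 0 in the shift tables, whatever its size, while the text of the appendix foresees grading in both directions. This follows from the stated rules alone. The assumed LLN values affect only where grade 0 begins, not the result for high values.

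Two analytes and one family of safety tables are affected, and only for subjects with high values. How many that would be cannot be estimated from the documents. The adverse event tables, the analysis sets and the primary endpoint are untouched. This is a minor correction worth making before the tables are programmed.

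The fibrinogen cut-off is a separate clerical matter. It is probably a typing slip, or a loss when the PDF was read, and with no protocol-required fibrinogen data it has no demonstrated consequence.

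**What to change.** In SAP Appendix B Table 2:

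1. Label the existing potassium and corrected calcium rows as low-direction.
2. Add a high-direction row for each, with cut-offs taken directly from the CTCAE v4.03 scale the SAP already cites. The documents do not reproduce those cut-offs, so none are proposed here.
3. In section 10.6.2, state that these two analytes get one shift table per direction, each with its own worst post-baseline grade, and that grade 0 means no criterion met in that direction.
4. As a clerical check, compare the grade 2 fibrinogen cut-off with the source file and correct it if needed, or delete the row if fibrinogen is not collected.

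The cost is a few lines in the appendix and a small edit to the shift-table program. Potassium, calcium and albumin are already in protocol Table 11, so no new data are needed.
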